Subjects for the EDFI-Cohort study will be recruited during 2019 and 2020 from Department of Surgery, Slagelse, and Zealand University Hospital, Køge. Subjects need to be diagnosed with rectal cancer and have received curative surgery (low anterior resection) with/without adjuvant (radiation/chemo) therapy. Subjects for this study are to meet the following inclusion criteria: Low anterior resection (e.g. not limited to total mesorectal excision (TME) or partial mesorectal excision (PME)), ability to communicate in Danish, adults (> 18 years of age), and American Society of Anaesthesiologists (ASA) score: I-IV. Exclusion criteria are: ASA score of: V-VI.

Prior to inclusion, subjects must provide written informed consent to participate in this study.

Subjects for the EDFI-Cohort study will be identified through surgical codes at Slagelse Hospital and Zealand University Hospital, Køge, Denmark. Eligible subjects will primarily be invited to participate in this study prior to discharge with oral and written information, provided in person by a health professional from the research group. Alternatively eligible subjects will be sent a letter after discharge. The letter and written information contain information on the study, the right to say no to the study, the right to 24 hours reflection time and the right to bring next of kin or another person of the subject's choice with him/her to the inclusion meeting. Potential subjects that are only invited by letter are asked to contact the research group for further information. A second letter will be sent to potential subjects whom have not contacted the research group within two weeks, and 2-3 weeks after the second letter has been sent, subjects will be contacted once by phone. Verbal and written information will be provided by a health professional from the research group at a meeting in an undisturbed examination room at Slagelse Hospital or Zealand University Hospital, Køge, Denmark.

Sample size:

The cohort will recruit all eligible patients from summer 2019 to April 2020. In this time period we estimate to recruit 70 patients to the EDFI cohort. A total of 86 patients were surgically treated for rectum cancer in 2017 at Slagelse Hospital and Zealand University Hospital, Køge.

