The minimal clinically important difference on the EORTC QLQ-C30 subscale Global Health Status is considered to be 7-12 points for a variety of cancer types (rectal cancer not studied). [19-22] Thus, with the estimated recruitment flow; we will have a power of 0.98 for a two-sample pooled t-test of a normal mean difference with two-sided significance level of 0.05 ($p \leq 0.05$), assuming a common SD of 22 EORTS QLQ-C30 points to detect a mean difference of 10 points between groups with different surgical techniques or with high or low anorectal muscle function (primary study purpose 1).

Additionally, we will have a power of 0.99 for a two-sample pooled t-test of a normal mean difference with two-sided significance level of 0.05 ($p \leq 0.05$), assuming a common SD of 12 LARS points [3] to detect a mean difference of 6 LARS points between groups with different surgical techniques or with high or low anorectal muscle function (study purpose 2).

Whether or not we are able to reach sufficient numbers within the 1 year timeframe, recruitment will end in April 2020.

Outcomes:

Outcomes is to be obtained from patient records, self-reported questionnaires and objective measures. For full list of outcomes to be collected and time points, see table 1.

Patient records:

In order to identify and invite eligible subjects, information on diagnosis, type of surgery, admission and contact information will be collected from patient records and given to the research group, prior to acceptance to participate in the study. After acceptance to participate in this study the following descriptive information will be collected from patient records (including electronic patient journals): Age at surgery (years), time of surgery (weeks), type of surgery, surgical complications, gender (male/female), tumor height (cm from anal verge), tumor stage (UICC), involvement of lymph nodes (N stage), additional radiotherapy/chemotherapy, surgical technique, anastomosis, ASA grade (I-IV), time with temporary stoma, and if available data from pre-surgery manometric examination, digital examination, Six-Minute Walk test (6MWT) and mortality status. This information will be used to adequately describe patient characteristics, cancer treatment, surgical outcome and mortality status. Additionally the acceptance to participate in this study allows the research group and relevant control agency direct access to collect information on health status in relation to quality control.

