Statistical analysis

We plan to analyze the EDFI-Cohort study as repeated measures with both simple and multiple linear regression models for the continuous data. We plan to adjust for the following known confounders: patient characteristics: age at surgery, gender, tumor height, tumor stages and variables related to treatment: surgical complications (e.g. nerve damage, sphincter rupture), additional radiotherapy/chemotherapy, time with stoma.

Patient involvement

Prior to planning of the EDFI-Cohort study, we have performed a single case-study (spring 2016) on examination procedure, questionnaires and pelvic floor muscle rehabilitation. This case provided us with valuable information on testing and possible evaluation of treatment effect. In the winter of 2017-18, we

interviewed subjects on their perspective on this study design and examination load. In the same time-period, we did pilot testing on the clinical examinations.

Research ethics

Examinations included in this study are all associated with very few, if any, adverse events, except from the mild discomfort related to the clinical anorectal examination itself. Subjects included in this study will receive four examinations, whereas care as usual at Slagelse and Køge Hospital usually include one examination/contact to the local LARS clinic with no anorectal examination. This, included subjects are more closely monitored and, if need be, might receive relevant treatment earlier compared to care as usual patients.

Future implications

Results from the EDFI-Cohort study will help guide the design of randomized controlled trials on treatments of faecal incontinence in subjects who have been surgically treated for rectal cancer. With emphasis on establishing the role of anorectal muscle function in the development of faecal incontinence.

Applicability of registrations and approvals

A prior version of the EDFI-Cohort study protocol has been approved by the regional research ethics committee of Region Zealand and The Data Protection Agency journal number: REG-130-2017. This project adhere to the General Data Protection Regulation and Data Protection Act. The regional research ethics committee and data protection agency will need to approve the new version of the study protocol prior to project start. Finally, the project will, prior to start, be registered at ClinicalTrials.gov. This study is part of the patient compensation scheme (patienterstatningsordningen).

Study economy

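### The stated t-test powers of 0.98 (quality of life) and 0.99 (LARS) do not follow from 70 patients: that test has at most 0.47 and 0.54, and the stated figures need about 300 patients

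*Protocol*

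**What the plan says.** All of the design figures stand in the protocol under Method, Sample size.

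- Size: "In this time period we estimate to recruit 70 patients to the EDFI cohort". For context it adds that "A total of 86 patients were surgically treated for rectum cancer in 2017" at the two hospitals.
- Primary outcome (QLQ-C30 global health status): "with the estimated recruitment flow; we will have a power of 0.98 for a two-sample pooled t-test of a normal mean difference", at a "two-sided significance level of 0.05", for a difference of 10 points with a common SD of 22. The important difference is put at 7 to 12 points.
- Secondary outcome (LARS score): "Additionally, we will have a power of 0.99 for a two-sample pooled t-test of a normal mean difference", at the same level, for a difference of 6 points with a common SD of 12.
- Groups: defined by surgical technique, or by high or low anorectal muscle function. No group sizes and no dropout rate are given.
- End of recruitment: "Whether or not we are able to reach sufficient numbers within the 1 year timeframe, recruitment will end in April 2020".

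The Statistical analysis section plans to analyse the data "as repeated measures with both simple and multiple linear regression models for the continuous data", with adjustment for a list of confounders. It gives no power figure of its own.

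**The concern.** The effect sizes are moderate: 10/22 = 0.45 and 6/12 = 0.50 standard deviations. Seventy patients divided into two groups cannot give power near 1 at effects of that size, so the stated figures looked wrong on sight. Test, significance level, SDs, differences and total number are all legible, so this can be settled by arithmetic.

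These are the only power figures for the primary and secondary outcomes. The Hypothesis section predicts differences in quality of life and LARS score between surgical techniques. A reader who takes 0.98 and 0.99 at face value would treat a non-significant technique comparison as near proof that no difference of the stated size exists. The protocol also says its results will guide the design of randomised trials.

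**Working it through.** **Inputs** (Protocol, Method, Sample size): total N = 70; two-sided alpha 0.05; quality of life, difference 10, SD 22; LARS, difference 6, SD 12. The split is not stated. I use 35:35, which gives the highest power of any split of 70, and show others as assumptions.

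**Formula.** For group sizes n1 and n2, the noncentrality is λ = (difference / SD) × √(n1·n2 / (n1 + n2)). Power is the probability that a noncentral t variable with n1 + n2 − 2 degrees of freedom exceeds the two-sided critical value in absolute size.

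**Attempt to reproduce the stated figures.** At 35:35, √(35 × 35 / 70) = 4.183, with 68 degrees of freedom and critical value 1.995.

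- Quality of life: λ = 0.4545 × 4.183 = 1.90; power **0.466** (stated 0.98).
- LARS: λ = 0.50 × 4.183 = 2.09; power **0.541** (stated 0.99).

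The normal approximation agrees: Φ(1.90 − 1.96) ≈ 0.48 and Φ(2.09 − 1.96) ≈ 0.55.

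**Other readings of the protocol's counts**

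| Reading | Quality of life | LARS |
|---|---|---|
| 70 in total, 35:35 | 0.466 | 0.541 |
| 70 in total, 50:20 (assumed) | 0.395 | 0.46 |
| 70 in total, 14:56 (assumed) | 0.323 | 0.378 |
| 70 in total, 35:35, one-sided 0.05 | 0.594 | 0.665 |
| 86 in total, 43:43 | 0.549 | 0.630 |
| 70 per group | 0.761 | 0.836 |
| 86 per group | 0.842 | 0.903 |
| **Stated** | **0.98** | **0.99** |

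**Patients needed for the stated powers, equal groups.** Quality of life 0.98: 157 per group, 314 in total. LARS 0.99: 148 per group, 296 in total. Allowing for rounding, both stated values appear together only at 150 to 165 per group (300 to 330 patients); at 150 per group the powers are 0.975 and 0.991.

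**Could the SDs be misprinted?** At 35:35 they would have to be about 10.5 and 6.0, roughly half the stated 22 and 12, for both outcomes at once.

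**Possible origin.** A one-sample or paired t-test on all 70 patients, using 22 and 12 as the SDs, gives 0.963 and 0.985. These are close to the stated values but do not match them. The whole cohort may have been entered into a one-sample formula, but this is not established, and it is not the test the protocol names.

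**What 35:35 does support**

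- Over the protocol's own 7 to 12 point range, quality-of-life power runs from 0.26 to 0.61.
- Differences detectable with 80% power: 14.9 quality-of-life points and 8.2 LARS points.
- Expected 95% confidence interval half-width, t(0.975, 68) × SD × √(2/35): 1.995 × 22 × 0.239 = 10.5 points and 1.995 × 12 × 0.239 = 5.7 points.

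**The case against.** The strongest reply is that the t-test is not the planned analysis. The protocol plans repeated-measures regression with six questionnaire time points. Manometry is measured on continuous scales, so a regression need not split it into high and low. The miss rates of 53% and 46% therefore describe a test nobody intends to run. This stands as a caveat: 0.47 and 0.54 are the powers of the stated test, not of the planned model.

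It does not rescue 0.98 and 0.99. The protocol attributes them to a t-test and gives no within-patient correlation. As an illustration on my own assumptions (mean of six visits, constant difference, equal correlation r between visits, nothing missing), the SD shrinks by √((1 + 5r)/6). At 35:35 the powers are then:

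| r | Quality of life | LARS |
|---|---|---|
| 0.5 | 0.69 | 0.77 |
| 0.3 | 0.83 | 0.89 |
| 0.2 | 0.90 | 0.95 |

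The stated values are reached only if r is at most about 0.07 (quality of life) or 0.10 (LARS).

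A second reply is that the sample size was not derived from the power: all eligible patients are invited and recruitment ends on a fixed date. That is true, and it means no operational decision turns on the error. It does not make the statement correct, and readers will still use it to interpret null results.

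**Conclusion.** The concern holds. For the test, SDs, differences and significance level the protocol states, 70 patients give power of at most 0.47 (quality of life) and 0.54 (LARS), not 0.98 and 0.99. The chance of missing the stated difference is 53% instead of 2% for quality of life, and 46% instead of 1% for LARS. The stated figures would need 314 and 296 patients. The result uses only the protocol's inputs plus an equal split and no missing data, both of which favour the protocol. No two-sample reading of its patient counts comes close. The 80% detectable quality-of-life difference, 14.9 points, lies above the whole range the protocol calls important. The power of the planned repeated-measures model remains unknown, because its correlation is not given. The figures must be corrected.

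**What to change.** Necessary change, under Method, Sample size: do one of the following.

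- Replace 0.98 and 0.99 with the power of the stated t-test at 70 patients: about 0.47 and 0.54 at 35:35, and lower for unequal groups (for example 0.40 and 0.46 at an assumed 50:20).
- Give the power of the planned repeated-measures model instead, stating the assumed within-patient correlation, group split and missing data.

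Alongside either, it would help to report the differences detectable with 80% power (about 15 quality-of-life and 8 LARS points) and the expected 95% interval half-widths (about 10.5 and 5.7 points), and to say that a non-significant comparison is not evidence of no difference.

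Optional and separate from the arithmetic error: add a row for lower recruitment, labelled as an assumption. At the 2017 volume of 86 operations a year, 9 to 12 months yields 64.5 to 86 operations. Seventy is therefore 109% to 81% of all of them, before restricting to low anterior resection and to those who consent. With 50 patients at 25:25 the powers are 0.35 and 0.41.

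Cost: wording only. Recruitment, visits and analyses stay as they are. The downside is that the stated power becomes much less favourable.

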Other factors that are likely to play a role in developing major LARS, has to our knowledge not yet been studied. In order to evaluate the underlying mechanisms of LARS, and in the future provide effective treatments, it is central to evaluate the anorectal muscle function. Anorectal muscle function has been evaluated with anorectal manometry in patients who have been treated with low anterior resection at a median of 6 weeks (range 4-40 weeks) [12] and at a mean of 23 months (range 6-106 months) [13, 14] after surgery. Despite variations in methodology, these studies had similar findings with anorectal resting pressure of 20-40 mmHg and maximal squeeze pressure of 80-140 mmHg, which is half the pressure performed by continent controls [12-16]. These studies have also measured rectal capacity. They found a maximal tolerated volume of 95-140 mL and around 200 mL measured in continent controls. Additionally, a conscious rectal sensitivity threshold of 35-44 mL was measured in both patients and continent controls. [12-16] Despite these findings, there is limited knowledge of the relationship between severity of faecal incontinence and pelvic floor muscle function in patients surgically treated for rectal cancer [17].

Despite LARS being a central factor for reducing quality of life, other factors are likely to play an important role as well. Dysfunctions such as sexual dysfunction, urinary incontinence and fecal incontinence are present in patients with rectal cancer as long after surgery as 4 years, therefore it is important to determine when these symptoms develop and how they are related to each other in patients treated for rectal cancer. [18] Other factors likely to reduce quality of life are problems with fatigue, physical inactivity and finding meaning in life. To our knowledge, no records exist on these relationships from prior to surgery to 2 years after. These softer factors are central to include when developing effective treatments strategies for this patient group.

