Digital examination of anorectal muscle function is an easy-to-use and cheap assessment tool readily available in a clinical setting. When using the Digital Rectal Examination Scoring System (DRESS) that ranges 0-5 (lowest to highest), the digital examination showed very high agreement with manometry pressures (Spearman rank correlation coefficients 0.81-0.82). [34] Digital examination involves inserting a finger in the anal canal.

High-Resolution AnoRectal Manometry (HR-ARM) is considered state of art in measuring anorectal muscle function and has shown to have moderate to high reliability in adults with or without faecal incontinence, with intra-individual correlations (ICC) for resting pressure (ICC 0.60-0.91) [35] [36] [16], squeezing pressure (ICC 0.49-0.95) [35] [36] [16] and rectal perception (ICC 0.75-0.92) [36] [16]. HR-ARM involves a narrow catheter being inserted in the anal canal that measures pressure with strain gauges several times throughout the anal canal. Rectal perception is measured by inflating a balloon in the rectal canal.

The Six-Minute Walk test (6MWT) is a widely used measure of submaximal exercise capacity in populations with and without pathology. [37] The 6MWT has shown to be correlated to maximum exercise capacity ($r=0.67$) and to perceived physical function (EORTC QLQ-C30 physical function subscale) ($r=0.55$) in cancer patients. [38] A systematic review has recommended that a minimal clinically important difference of ≥ 30.5 m for the 6MWT can be considered clinically meaningful for patients with a variety of pathology. [39] 6MWT involves the patient walking as far as possible in 6 minutes indoor.

Table 1: Full list of outcomes.

Patient records at hospital	Items that is obtained	Time point
Descriptive information:	Age at surgery (years) Time of surgery (weeks) Gender (male/female) Tumor height (cm from anal verge) Tumor stage (UICC) Involvement of lymph nodes (N stage) Additional radiotherapy/chemotherapy Surgical technique Anastomosis ASA grade (I-IV) Time with temporary stoma Manometric examination (if available) Digital examination (if available) Six-Minute Walk test (if available)	At identification of relevant patients
Adverse events from surgery	Hospitalisation 30 days after surgery Surgical complications	30 days after surgery
Mortality (and at the National Patient Registry)	Is the subject deceased?	If no answer is obtained through questionnaires or no show at clinical examination.

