Self-reported outcomes:	Questionnaire	Time point
Education level, work status and civil status	Non standardized questionnaire	3 weeks
Bowel related quality of life	Low anterior resection symptom – score (LARS-score)	3, 6, 12, 26, 52 and 104 weeks
Faecal incontinence	St. Marks Incontinence score (Vaizey-score)	3, 6, 12, 26, 52 and 104 weeks
Quality of life of cancer patients:	EORTC QLC-C30	3, 6, 12, 26, 52 and 104 weeks
Colorectal	EORTC QLQ-CR29	3, 6, 12, 26, 52 and 104 weeks
Fatigue	EORTC QLQ-FA12	3, 6, 12, 26, 52 and 104 weeks
Information about disease and treatment	EORTC QLQ-INFO25	3, 6, 12, 26, 52 and 104 weeks
Urinary Incontinence	International Consultation on Incontinence Modular Questionnaire (ICIQ) - Urinary Incontinence Short Form (ICIQ-UI SF)	3, 6, 12, 26, 52 and 104 weeks
Urinary symptoms, males	ICIQ-Male Lower Urinary Tract Symptoms (ICIQ-UI MLUTS)	3, 6, 12, 26, 52 and 104 weeks
Urinary symptoms, females	ICIQ-Female Lower Urinary Tract Symptoms (ICIQ-UI FLUTS)	3, 6, 12, 26, 52 and 104 weeks
Sexual dysfunction		

	Sexual dysfunction, males	ICIQ-Male Sexual Matters associated with Lower Urinary Tract Symptoms (ICIQ-UI MLUTSsex)	3, 6, 12, 26, 52 and 104 weeks
	Sexual dysfunction, females	ICIQ-Female Sexual Matters associated with Lower Urinary Tract Symptoms (ICIQ-UI FLUTSsex)	3, 6, 12, 26, 52 and 104 weeks
	Physical activity level	physical activity section of the Danish National Health Profile	3, 6, 12, 26, 52 and 104 weeks
	Sources of meaning and meaningfulness	Sources of Meaning and Meaning in Life Questionnaire (SoMe)	3, 6, 12, 26, 52 and 104 weeks

Objective measure:	Units:	Time point
Anorectal muscle function (digital examination)		
Maximal resting pressure Maximal squeeze pressure Endurance squeeze - max squeeze pressure or longest time Latency (rate of force development), number of rectal muscle contractions/squeezes in 15 sec test.	0-5 (DRESS) (lowest to highest) 0-5 (DRESS) (lowest to highest) 0-5 (DRESS) and s, maximum of 60 s. n	6, 26, 52 and 104 weeks
Anorectal muscle function (High-Resolution AnoRectal Manometry)		
Pressure measurements: Maximal resting pressure Maximal squeeze pressure Maximal squeeze pressure duration	mmHg mmHg s	6, 26, 52 and 104 weeks
Volume capacity measurements: Maximal tolerated volume Conscious rectal sensitivity threshold Conscious rectal sensitivity Constant sensation	mL mL % of maximal volume mL	6, 26, 52 and 104 weeks
Physical Performance		
6-Minute Walk test	M	6, 26, 52 and 104 weeks

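### Power for the muscle-function contrast rests on undefined high and low groups, although pressure is recorded in mmHg and the planned regression could use it as a continuous predictor

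*Protocol*

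**What the plan says.** The Sample size section (Protocol, Method) supports the quality-of-life aim with this claim: "we will have a power of 0.98 for a two-sample pooled t-test of a normal mean difference". The test is two-sided at 0.05 and the SD is taken as 22 points. The contrast that this power refers to is worded as follows: "to detect a mean difference of 10 points between groups with different surgical techniques or with high or low anorectal muscle function". For LARS it states "we will have a power of 0.99 for a two-sample pooled t-test", with SD 12, a 6-point difference and the same two kinds of grouping. The expected cohort is 70 patients in total.

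Table 1 lists the manometric pressure measures as "Maximal resting pressure Maximal squeeze pressure Maximal squeeze pressure duration", in mmHg, mmHg and seconds. It also lists volume and sensation measures (mostly mL), the digital examination score (0-5) and a contraction count, all at four visits.

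The Purpose asks how muscle function, among other baseline variables, predicts quality of life and LARS. Hypothesis 2 speaks only of poor function. The Statistical analysis section plans simple and multiple linear regression with repeated measures. None of these three places gives a cut-off, names a deciding measure or mentions splitting muscle function.

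**The concern.** The power sentences are the only place where the protocol says how muscle function would enter a comparison, and there it is two groups. Many measures at four visits could define those groups, so their membership and sizes are open. The regression in the Statistical analysis section needs no groups, so the quantity powered is not clearly the quantity to be estimated.

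If the two-group contrast is carried into the analysis, information is lost without any gain. Recruitment ends in April 2020 whatever the number reached, so extra patients cannot make up for it. A high-versus-low difference tied to one cohort's cut-off is also harder to carry into the randomised trials that the study is meant to inform than a difference per mmHg.

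**Working it through.** **Inputs.** From the Sample size section: n = 70 in total, two-sided alpha 0.05; quality of life difference 10 and SD 22; LARS difference 6 and SD 12. Group sizes are not stated, so 35:35 is taken as the most favourable case. Assumed: a normally distributed predictor, a linear relation, one time point, no covariates and no dropout.

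**1. The protocol's own figures.** For a pooled t-test with 35 per group (68 df), the noncentrality is difference / (SD × √(2/35)).
- Quality of life: 10 / (22 × 0.239) = 1.90, power 0.47 (stated 0.98).
- LARS: 6 / (12 × 0.239) = 2.09, power 0.54 (stated 0.99).

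The stated powers do not reproduce for the stated test. Even 70 per group gives only 0.76 and 0.84. That is a separate error in the same sentences and is not counted in the size of this point.

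**2. Information kept by a split.** When a share p of a normal predictor is called low, the fraction of information kept is φ(z_p)² / [p(1 − p)]. At the median this is 2/π = 0.637.

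| Split low:high | Kept | Lost | Equivalent n of 70 |
|---|---|---|---|
| 50:50 | 0.637 | 36% | 45 |
| 60:40 | 0.622 | 38% | 44 |
| 70:30 | 0.576 | 42% | 40 |
| 80:20 | 0.490 | 51% | 34 |
| 90:10 | 0.342 | 66% | 24 |

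**3. The association implied by the protocol's difference.** The halves of a standard normal predictor differ by 2√(2/π) = 1.596 SD, so the slope per SD is b = difference / 1.596. The residual SD is √(SD² − b²(1 − 2/π)).
- Quality of life: b = 10/1.596 = 6.27. Residual SD = √(484 − 39.3 × 0.363) = 21.67. Total SD = √(469.7 + 39.3) = 22.56. r = 6.27/22.56 = 0.278.
- LARS: b = 6/1.596 = 3.76. Residual SD = √(144 − 14.1 × 0.363) = 11.78. Total SD = √(138.9 + 14.1) = 12.37. r = 0.304.

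**4. Power with the same association, n = 70 (20,000 simulated cohorts).**

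| Outcome | Continuous predictor | Median split |
|---|---|---|
| Quality of life | 0.65 | 0.46 |
| LARS | 0.73 | 0.53 |

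The split results agree with step 1 (0.47 and 0.54).

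**5. Uneven groups.** If the difference is held at 10 with SD 22, t-test power is 0.32 at 56:14 and 0.20 at 63:7. If the slope of step 3 is held instead, the group difference grows as the split moves outward. At 80:20 it is 6.27 × 0.280 / 0.16 = 10.97, with within-group SD √(22.56² − 6.27² × 0.490) = 22.13, and power is 0.37. Either way it is below the median split.

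**The case against.** The strongest reply is that a two-group power sketch is a common simplification and not the analysis. The high/low wording appears only in the power sentences, not in the Purpose or the hypotheses, and linear regression is already planned. This stands. No section commits to splitting muscle function, so the loss above is what would follow from analysing the powered contrast and is not an established loss in this study.

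A cut-off and the choice of measure could also be set in an SAP that is not at hand. That is fair, and a missing cut-off alone would be no finding. But the protocol itself rests its power on a two-group contrast that does not match its planned regression, and that can be corrected where it is written.

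The power figures also ignore repeated measures and adjustment, so they show the relative cost of splitting and not the study's actual power. Table 1 includes an ordinal 0-5 score, for which grouping is less clearly wasteful. The argument concerns the measures in mmHg.

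Two stronger readings are tempting and are not supported:
- The Background gives patients' resting pressure as 20-40 mmHg and squeeze pressure as 80-140 mmHg, "which is half the pressure performed by continent controls". A reader might infer that nearly every patient would be called low. But the protocol never proposes control values as the cut-off and gives no SD. The share called low runs from about 50% (mean 40, cut at 40 mmHg) to over 99% (cut at twice the patient mean, assumed coefficient of variation 0.3). The patients' own ranges could equally support a balanced split.
- The Objective measures section reports "squeezing pressure (ICC 0.49-0.95". A reader might count misclassification around a cut-off against the split. Measurement error also flattens a continuous slope, so it does not favour one coding by itself.

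**Conclusion.** The point holds as a mismatch that should be corrected, not as a proven loss. The protocol powers an undefined high-versus-low contrast, records pressure in mmHg, and plans a regression without saying how muscle function is coded. If the split is what is analysed, the best case (median, roughly normal predictor) discards 36% of the information, worth about 25 of 70 patients (70 − 45). Power falls from about 0.65 to 0.46 for quality of life and from about 0.73 to 0.53 for LARS. These figures assume linearity, one time point, no adjustment and complete data on 70 patients. A continuous predictor does not rescue the stated 0.98 and 0.99.

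**What to change.** - In both power sentences and in the Statistical analysis section, state that muscle function enters the planned regression as a continuous predictor. One example is resting and squeeze pressure from high-resolution manometry, reported as the difference in quality of life or LARS per 10 mmHg or per SD.
- Restate the power for the muscle-function aim on that basis, with the assumed slope or correlation and the cohort size.
- Show high/low groups only descriptively, and give the cut-off used.

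The cost is rewording and one new power calculation. No visit, measurement or patient is added. The small downside is a linearity assumption, which can be checked by plotting the outcome against pressure.
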